2. Remainder of data stored in the database include the unique study ID, age, sex, race, ethnicity, all lab results (as described in Procedures section 10.1), nutrition screening results (as described in Procedures section 10.2), symptom and function survey (section 10.2) and physical exam findings (section 10.2). For symptomatic veterans who are started on thiamine repletion, the symptom and function survey and physical exam findings will be repeated at visit 3 and recorded in the database.

Paper records of data include:

1. Patient name and hospital room number.
2. All study data will be recorded on paper and stored in locked file cabinets within the locked research department.

Sharing of Results with Participants

Thiamine and other micronutrient results will be shared with Veteran participants and will be available for them to view in their electronic medical record. For Veterans found to have low thiamine levels, we will call the veteran and start them on thiamine tablets if they haven't already been started on them. We will notify their primary care doctor as well to ensure ongoing thiamine repletion after the study has concluded.

Withdrawal of Participants

We do not anticipate withdrawing participants from our study without their consent. Participants may withdraw from the study voluntarily at any time by in person meeting or telephone contact with study managers. The Principal Investigator also reserves the ability to early exit subjects from the study at any time in the event a subject is non-compliant with study visits any other component of the study. This will be exercised at the discretion of the PI only after multiple contact attempts have been made and a certified letter sent to the subject.

Approach to Analysis:

All data will be analyzed by a statistician affiliated with the VA research department trained biostatistician. The data will be analyzed using the statistical software SAS on the VA Informatics and Computing Infrastructure (VINCI).

15.1 Prospective cohort study to determine the prevalence and risk associations of TD.

Measurements: The **primary outcome** of this study is to measure the prevalence of TD as defined by abnormally low or low normal thiamine biomarkers combined with symptoms that respond to thiamine replenishment. **Secondary outcomes** will include describing demographic, clinical, and nutritional characteristics among those with and without TDDs. A TDD will be defined as an acute condition with symptoms that are known to be due to TD and that improve with adequate thiamine replenishment.

Statistical analysis/power calculations: Our primary endpoint is the prevalence of TDDs which we will compute as the proportion of TDD cases over the total number of subjects enrolled. Given the feasibility of this study and our patient population, we believe we can enroll and follow 300 subjects over a one-year enrollment period with an anticipated drop-out rate of 15%. Current best estimates for TD in similar populations are approximately 25%^{19,24,27}. Such an enrollment would provide us with a precision of TDD prevalence of +/- 5.4%. A sample size of 300 and estimated drop out of 15% leaving 255 subjects would provide us with 81% power to detect an 8% absolute difference from this expected prevalence. To explore differences in demographic, clinical, and nutritional characteristics among those with and without TDDs, continuous variables will be compared by T-test unless parametric assumptions are not met in which case a Kruskall-Wallis test will be used. Categorical variables will be evaluated through Chi-square or Fishers exact test depending on assumptions being met. We will estimate prevalence rate ratios for association factors. If the prevalence is achieved, we estimate that we would have adequate numbers to identify a range of different rates of exposure variables among TDD and non-TDD patients. For example, with 63 TDD and 192 non-TDD patients and a 10% rate of a given explanatory variable, we would have 80% power to detect prevalence rate ratios of ~2.5 and higher in bivariate analyses.

15.2 Open label treatment study to develop standardized case definitions of treatment responsive TDDs and correlate with thiamine biomarker levels to determine clinically relevant cut-points of those biomarkers.

Measurements: The **primary outcome** of this arm is to describe the prevalence of treatment responsive TDD symptoms in the hospitalized Veteran population. The **secondary outcome** is to explore cut-points of thiamine biomarkers that can be utilized to diagnose TDDs with more sensitivity than current clinical laboratory limits.

Statistical analysis: Descriptive features of treatment responsive TDD patients will include frequencies of symptoms, physical exam findings, and functional disability compared to patients without TDDs. We will describe each case's initial signs and symptoms and improvements. To better define the thiamine levels that differentiate thiamine responsive from thiamine non-responsive symptoms, the levels of thiamine will be compared between groups using Kruskal-Wallis test corrected for multiple comparisons. For the two thiamine biomarkers, the optimal cut-point to distinguish between thiamine responsive and thiamine non-responsive symptoms will be determined by applying the Liu method⁴⁷ to maximize the product of the sensitivity and specificity. Based on the cut-points, thiamine levels will be dichotomized into lower and higher or equal to the cut-point and the area under the receiver-operating curve (AUC), the sensitivity, specificity, positive and negative predictive values, and the likelihood ratio will be computed. These cut-points will be compared to that of the current laboratory reported abnormal cut-points. For this aim the power to identify discriminating cut-points will be dependent up on the prevalence of the treatment responsive disorder and the distribution of thiamine levels. Under conservative assumptions (alpha 0.05, beta 0.80) and a 2 to 1 ratio of negative responders to positive responders at a given thiamine cut-point level, we would need 19 responders and 38 non-responders for a given symptom to estimate an area under the curve (AUC) of 0.725 compared to a null AUC of 0.50. While there is no information to inform the reasonableness of these parameters, we believe we will have reasonable ability to explore thiamine level cut-points for treatment responsive TDD for this exploratory aim.

4.3 Nested case-control study to determine if inflammation is associated with the presence of TD in hospitalized veterans.

Measurements: The **primary outcome** of this arm is to determine if there are differences in markers of inflammation as evidenced by hs-CRP and fibrinogen between TDD and non-TDD hospitalized Veterans. Presence of inflammation will be defined as hs-CRP higher than upper limits of normal 0.75 milligrams/deciliter (mg/dL), or fibrinogen higher than the upper limits of normal 471 mg/dL. Individuals will also be considered to have inflammation if they are diagnosed with one of the AICs or CICs previously described.

Statistical analysis: The presence or absence of AICs and CICs among those with and without TD (defined as treatment responsive TD or abnormal thiamine levels based on clinical laboratory standards) will be evaluated by Chi-square or Fisher's exact test depending on assumptions being met. An assessment of total number of AICs and/or CICs between TD and non-TD patients will be assessed using the student's T-test or non-parametric methods depending on necessary assumptions being met. To evaluate if biomarkers of inflammation (hs-CRP and/or fibrinogen) are associated with presence or absence of TD we will compare levels between these two groups. If group sizes are large enough, we will attempt to develop exploratory multivariate models to identify AICs, CICs, and inflammation markers which are associated with TDD status. As no studies have reported on inflammatory markers, AICs, and CICs and thiamine deficiency, this is an exploratory aim for which we have no data to estimate a priori sample size requirements.

Resources Available

The VA hospital is a 64-bed general medical and surgical facility. There are typically 10 patients admitted to the hospital daily and we expect no trouble enrolling 300 patients in our study over 12 months. [name] will dedicate 3/8ths of her full-time employment with the VA managing this project. We will have a full-time research coordinator and a half time Health Systems Specialist (PA or ARNP) performing the day-to-day operations of the study. [name] will train both employees on the research purpose and protocol and assign duties as appropriate to their background and training in completion of the study. Veteran participants will be given a detailed description of their role in the research project and will be provided phone numbers to contact study personnel in the event of an adverse outcome or symptom. All medical and psychological care will be provided through the VA for adverse events.

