Aim 2: Through an open label treatment study, we will define thiamine deficiency disorders (TDDs) as cases with low or “low normal” thiamine levels and symptoms of TD that improve with thiamine replenishment. Hypothesis 2: The current bioassays of thiamine do not accurately define TDDs and individuals with results the “low normal” range will show symptom improvement with thiamine replacement.

Aim 3: Utilizing a nested case control study design, determine if acute and chronic inflammatory conditions with elevated biomarkers of inflammation increase the risk of developing TDDs. Hypothesis 3: Acute and chronic forms of inflammation cause oxidative stress which increase basal requirements for thiamine as a metabolic cofactor and increase the risk of developing TDDs.

Study Population:

We anticipate 300 patients will be enrolled in this study with an age range of 18 and older. There will be no exclusions due to gender, race, age, or ethnicity. We will endeavor to include women and minorities to the extent possible based on the inpatient population which historically has been predominantly male (95%) and white (90%). All subjects recruited for this study will be Veterans admitted to inpatient units at VA Sierra Nevada Healthcare System hospital (single site recruitment). There will be no minor children participating. The health status will be compromised from mild to severe due to the nature of being hospitalized. We will not include adults unable to consent (those who are cognitively impaired with Impaired Decision-Making Capacity). We will not enroll pregnant women as we do not admit them to the VA hospital due to lack of maternity services.

Inclusion criteria:

- anyone age 18 or older requiring full hospital admission to the medical service.

Exclusion criteria:

- excess alcohol intake as defined by the National Institute of Alcohol Abuse and Alcoholism as more than 14 standard drinks per week for men less than age 65, or more than 7 drinks per week for women or men 65 years of age or older
- unable to consent due to impaired decision making capacity.
- veterans who live more than 75 miles from the study site as that would likely hinder their ability to attend follow up visit 3.
- Veterans who suffer from quadriplegia because they cannot participate in the physical assessments
- Veterans taking thiamine supplements

Vulnerable Populations:

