The population enrolled may include vulnerable populations such as those with memory loss or neuropsychiatric symptoms that may be a result of thiamine deficiency. Through this research we hope to find potential treatments for these conditions which are disabling. We will assess their decision-making capacity during the consent process utilizing the U-ARE Protocol⁴⁵.

Sample Size:

Current best estimates for TD in similar populations are approximately 25%^{19,24,27}. Such an enrollment would provide us with a precision of TDD prevalence of +/- 5.4%. A sample size of 300 and estimated drop out of 15% leaving 255 subjects would provide us with 81% power to detect an 8% absolute difference from this expected prevalence.

Recruitment Process:

We will apply for a HIPAA waiver to preliminarily review charts of newly admitted Veterans for eligibility. Each workday, we will obtain a list of veterans newly admitted to the hospital from administration since the previous workday (on the first workday of a week, this will include weekend admissions). We will not use advertising to recruit potential participants. For those who do not have exclusion criteria, we will approach the patient to discuss the study and determine if they have capacity to consent to the study. If they lack capacity at the time we approach them, we will discuss with the treatment team whether the lack of capacity is expected to be temporary, due to their acute medical condition, or permanent due to underlying neuropsychiatric disease. If it is deemed temporary, we will approach the patient later in the hospital stay when their acute conditions have

been treated and discuss the study again to see if their capacity has improved to a degree where informed consent is possible.

Screening Procedures:

The research coordinator will preliminarily review charts for exclusion criteria.

Informed Consent Process:

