10 STUDY INTERVENTIONS

Table 3: Study procedure schedule of evaluations

	Visit 1- early hospitalization	Visit 2 – late hospitalization	Visit 3 – after 2 weeks of thiamine repletion
Chart review for social and medical histories	X		
Symptom and function survey		X	X
Targeted physical exam		X	X
Nutritional history		X	
Lab draw for thiamine biomarkers	X		X
Blood draw for prealbumin , others as needed	X		
Thiamine repletion	X ¹	X ²	

1. For select patients with WE or severe symptoms of thiamine deficiency 2. all others

10.1 Visit 1 – initial hospital encounter: The Veteran's chart will be reviewed for acute and chronic medical problems, habits, and social history. We will schedule lab testing (as described below) to coincide with routine morning blood draw to avoid additional phlebotomy. For those who present with symptoms of Wernicke's encephalopathy (WE) which requires urgent parenteral thiamine replacement, we will perform our history and exam promptly and advise the primary inpatient treatment team to initiate therapy if they meet the Caine criteria⁴⁶ for WE. For all others who do not have evidence of WE, we will proceed to visit 2.

Thiamine biomarker and other micronutrient assessment: Fasting plasma thiamine levels and whole blood ThDP will be ordered for collection by lab personnel as soon as feasible after consent is obtained from the Veteran. We will also order blood levels of vitamins B12, D, and folic acid as well as prealbumin if not done via routine care within the preceding four weeks. In addition, we will extract albumin, complete blood count, and magnesium as ordered by the primary team as part of routine care. There will be no genomic sequencing, in whole or in part, as part of this analysis. Blood specimen will be collected as part of routine medical care by laboratory personnel. Lab tests not routinely run in our local laboratory will be sent out to reference labs per the usual practice of the Department of Pathology. There will be no direct handling of blood specimen by the research team. Results of the lab tests will be available in a participant's electronic medical record and will be extracted by the study coordinator and stored in a de-identified database. If they have been prescribed thiamine replenishment and the thiamine lab values are lost, we will include the remaining data gathered in the study.

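### Nothing ensures or records that the Visit 1 thiamine sample precedes the first thiamine dose, and no rule says how a post-dose level is classified

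*Combined protocol and SAP*

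**What the plan says.** **Sample.** Section 10.1 states: "We will schedule lab testing (as described below) to coincide with routine morning blood draw". The two thiamine assays "will be ordered for collection by lab personnel as soon as feasible after consent is obtained from the Veteran".

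**Early treatment.** Table 3 marks repletion at Visit 1, and its first footnote limits this to a subgroup: "For select patients with WE or severe symptoms of thiamine deficiency". Section 10.1 describes WE as a condition "which requires urgent parenteral thiamine replacement" and says of such Veterans: "we will perform our history and exam promptly and advise the primary inpatient treatment team to initiate therapy". The blood draw is not placed in that sequence.

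**Survey and exam.** Table 3 puts these at Visits 2 and 3 only. Section 10.2 delays the Visit 2 assessment until the acute illness is stable, and places the advice on intravenous thiamine for severe symptoms or WE alongside the Visit 2 exam.

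**Late consent.** Under Recruitment Process, if incapacity is judged temporary, "we will approach the patient later in the hospital stay", once acute conditions have been treated.

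**Exclusion.** The criterion reads "Veterans taking thiamine supplements". It does not mention thiamine given in hospital.

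**Compromised values.** The only rule, in 10.1, covers thiamine results that are lost. The list of stored data under Data and Specimen Banking names no dose or draw times.

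**The concern.** A biomarker meant to show deficiency is interpretable only if one knows whether thiamine was given before the sample. Two groups can be sampled after a dose: Veterans repleted at Visit 1, and Veterans consented late after the hospital team has already treated them. They are likely to include some of the most symptomatic participants.

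Three results are at stake.

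- **Prevalence (15.1).** A deficient Veteran whose level has risen to normal after a dose would fail the biomarker part of the primary outcome.
- **Cut-points (15.2).** A responder would enter with a level that no longer reflects the deficiency.
- **Hypothesis 2.** A low level raised by a dose into the low-normal range would look like support for the claim that low-normal Veterans respond.

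Without recorded times, none of this could be detected at analysis.

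**Working it through.** **1. The plan's own figures.** Inputs from 15.1: expected prevalence 25%, 300 enrolled, 15% drop-out, 255 remaining, precision ±5.4 points, 81% power for an 8-point difference.

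- Wald half-width at n = 255: 1.96 × √(0.25 × 0.75 / 255) = 5.31 points. At n = 300 it is 4.90. The mean Clopper-Pearson half-width at n = 255 is 5.49. The stated 5.4 therefore fits about 255 subjects.
- Power at n = 255 for 25% against 33%, two-sided 0.05 (assumed, since 15.1 gives no alpha for this calculation), normal approximation: 81.9%. This agrees with the stated 81%.

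Neither figure is in dispute. They give the scale for what follows.

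**2. How a truly deficient Veteran with a normal post-dose level would be classified**

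| Place | Requirement | Result |
|---|---|---|
| 15.1, primary-outcome sentence | Low or low-normal level, and response | Fails |
| Aim 2 | Low or low-normal level, and improvement | Fails |
| 10.3, who is seen at Visit 3 | Low level, or low-normal level with symptoms | Not named |
| 15.1, TDD definition | Symptoms that improve; no biomarker | Case, if response is assessed |
| Section 4.3, nested case-control | Responsive TD or abnormal level | Case, if response is assessed |

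The outcome depends on which definition the analyst applies and on whether the Veteran is seen at Visit 3.

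**3. Size of the effect on prevalence.** The share of early-treated true cases is not in the documents. Let f be the share of the cohort who are true cases treated before the draw, and m the fraction of them missed. Both are assumed. Starting from the plan's 63 of 255 = 24.7%:

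observed prevalence = 24.7% − f × m

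| f | m = 0.5 | m = 1 |
|---|---|---|
| 1% | 24.2% | 23.7% |
| 2% | 23.7% | 22.7% |
| 5% | 22.2% | 19.7% |
| 10% | 19.7% | 14.7% |

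The understatement runs from 0.5 to 10 points. Each missed case costs 1/255 = 0.39 points. Matching the stated precision takes 0.054 × 255 = 13.8, or about 14 missed cases (0.054 × 300 = 16.2 if all enrolled are counted). The 10-point end is extreme: 25.5 missed cases would be 25.5/63 = 40% of all expected cases.

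**4. Cut-points.** Section 15.2 is sized on 19 responders and 38 non-responders for a given symptom. If two of the 19 sit above the cut-point only because they were sampled after a dose, apparent sensitivity falls by 2/19 = 10.5 points.

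**The case against.** Several points on the other side are sound.

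- **Baseline.** A reader might infer that severe cases are routinely surveyed and examined only after treatment. The text does not support that. For suspected WE, 10.1 puts history and exam before the advice to treat, and 10.2 places the intravenous advice with the Visit 2 exam. Only Table 3 and its first footnote suggest otherwise, so this is a conflict between table and text. A treated baseline remains possible for late-consented Veterans.
- **Classification.** A reader might also infer that the plan classifies post-dose samples as if untreated. No passage says so; the plan is silent. The TDD definition in 15.1 and the either-or definition in section 4.3 can capture a responder whose level is normal. Section 10.2 continues oral thiamine to Visit 3 in the intravenous group, and Study Duration has symptomatic Veterans finish at Visit 3, so response may well be observed.
- **Safeguards.** The sample is ordered promptly after consent, and the supplement exclusion may remove some pre-treated Veterans. If it does, however, it takes likely cases out of the prevalence estimate, which also needs stating.
- **Frequency.** It is wholly assumed. Most participants are sampled at Visit 1 and start oral thiamine at or after Visit 2, so only a subgroup is affected. Nor do the documents show how far an early dose raises either assay before the draw.

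These points limit the claim to possible misclassification in a subgroup of unknown size. They do not supply the missing rule: the primary-outcome sentence, read literally, still makes such a Veteran a non-case, and capture under a looser definition would send a post-dose level into the cut-point analysis.

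**Conclusion.** The gap is real and worth closing. The plan neither secures nor records draw-before-dose for Veterans repleted at Visit 1 or consented late, and has no rule for post-dose levels. Misclassification of true cases is possible, not certain, and would lower prevalence under the primary-outcome sentence. If 1% to 10% of the cohort are early-treated true cases and half to all are missed, the understatement is 0.5 to 10 points; at the low end it is minor against ±5.4. The existence of the gap rests on the text; its size rests entirely on assumption. The documents do not support the stronger conclusion that the clearest cases will be counted as non-deficient.

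**What to change.** Treatment and its timing stay as they are.

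1. **Record times.** At chart review, capture the date and time of the first thiamine-containing product since presentation, of the study draw, and of the baseline survey and exam. State whether in-hospital thiamine falls under the supplement exclusion.
2. **Cut-points (15.2).** Leave out every post-dose sample, whatever its value. Dropping only the values that are not low would discard qualifying low-normal results and keep post-dose lows selectively.
3. **Prevalence (15.1).** Do not take a post-dose level above low-normal as evidence of no deficiency; treat it as biomarker-unknown. Report prevalence in all enrolled and again with all post-dose-sampled Veterans removed. Add bounds that count the unknowns as all non-cases and then all cases. The bounds differ by the number unknown divided by the number analysed; 13 of 255, for example, gives 5.1 points.
4. **Baseline.** Reconcile Table 3 and its first footnote with 10.1 and 10.2 on when the survey and exam occur relative to repletion. Flag any post-treatment baseline in the response analysis. An acute-phase survey should not simply replace the Visit 2 baseline, because 10.2 delays that assessment to keep acute-illness symptoms from being mistaken for TDD.

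**Cost.** Two or three extra chart fields, a few Veterans unclassifiable on biomarkers, and slightly fewer subjects for the cut-points. The estimate with post-dose-sampled Veterans removed may describe a less severely ill cohort, which is why the bounds belong beside it.

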The principal risks to the patient are those associated with phlebotomy, namely discomfort and bruising associated with a needle stick. All efforts will be made to combine our tests with routine phlebotomy draws ordered by the primary treatment team. In some cases, additional time spent with investigators performing interviews and physical exams may cause psychological distress. In cases where thiamine is prescribed to treat suspected thiamine deficiency, there are rare instances of adverse reaction to parenteral thiamine such as anaphylaxis, pruritis, and local inflammation. Oral thiamine is typically well tolerated, the main difficulty is possibly having trouble swallowing tablets. There are extremely rare instances of side effects such as flushing, hives, itching, weakness, sweating, nausea and restlessness.

Protection Against Risk: The risk of bleeding or bruising due to phlebotomy will be mitigated by combining our specimen collection with routine collections placed by the primary treatment team to avoid extra phlebotomy. Only qualified personnel will draw blood. For psychological stress suffered, the Veterans will be assured they may refuse and withdraw from the study at any time if it becomes too burdensome. For instances where parenteral thiamine is ordered, it will be in a hospital setting where prompt medical attention is available should anaphylaxis or other side effects occur. For Veterans prescribed oral thiamine replacement who have difficulty swallowing tablets, a pill crusher will be provided. Any adverse reactions to parenteral or oral thiamine repletion will be recorded and replenishment discontinued.

Confidentiality Risks: Every effort will be made to keep all research information obtained from blood samples confidential, but absolute confidentiality cannot be guaranteed. Laboratory data obtained from blood samples will appear in the medical record for review by VA medical providers. The research information obtained as a result of participation in this study will be included in the medical record and may be given to primary care doctors. Information from which participants may be personally identified will be maintained in a confidential, locked file and will not be disclosed to third parties except with participant permission or as may be required by law.

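### Section 10.1 does not require the thiamine blood draw to precede the first IV dose, so a post-dose level can be recorded as the untreated baseline

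*Combined protocol and SAP*

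**What the plan says.** Table 3 of the combined protocol and SAP marks the thiamine biomarker draw at Visit 1. It also marks thiamine repletion at Visit 1, limited by footnote 1: "For select patients with WE or severe symptoms of thiamine deficiency". The table gives no order within the visit.

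Section 10.1 times the draw in two ways. The general sentence is "We will schedule lab testing (as described below) to coincide with routine morning blood draw to avoid additional phlebotomy". The sentence specific to thiamine asks for a fasting plasma level and whole blood ThDP, which "will be ordered for collection by lab personnel as soon as feasible after consent is obtained from the Veteran". Risk to Participants repeats the preference for shared draws: "All efforts will be made to combine our tests with routine phlebotomy draws ordered by the primary treatment team".

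For participants with symptoms of WE, 10.1 calls parenteral replacement urgent and says "we will perform our history and exam promptly and advise the primary inpatient treatment team to initiate therapy". Blood is not mentioned in that sentence. Everyone else is routed onward: "For all others who do not have evidence of WE, we will proceed to visit 2". Section 10.2 gives the IV regimen for severe symptoms or WE as 400 mg every eight hours for nine doses.

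The one data rule nearby is in 10.1. Where thiamine has been prescribed and "the thiamine lab values are lost, we will include the remaining data gathered in the study".

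**The concern.** A baseline biomarker is useful here only if it reflects status before treatment. The primary outcome in 15.1 counts thiamine deficiency when a low or low-normal biomarker is combined with symptoms that respond to replacement. If the sample follows IV dosing and the level has risen above the low-normal range, a true case fails the biomarker half of that definition.

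Section 15.2 is also exposed. It uses thiamine levels to separate responsive from non-responsive symptoms and to choose cut-points. A post-dose value would enter that analysis unmarked, as if untreated. A truly low participant whose post-dose level reads low-normal, and who then improves, would also appear to support Hypothesis 2. An untreated level cannot be recovered once dosing has begun, and those affected would be among the most severely ill.

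**Working it through.** No stated figure in the plan depends on this point, so the check is mainly one of sequence.

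**Order of draw and dose (WE route).**
- Draw: tied to the routine morning draw, or to the earliest practical time after consent (10.1).
- Dose: urgent, advised after a prompt history and exam (10.1).
- Link between the two: none in Table 3, 10.1 or 10.2.
- Staff contact: "Each workday, we will obtain a list of veterans newly admitted to the hospital" (Recruitment Process). A participant first seen during the working day could therefore be dosed that day and sampled the next morning.
- Safeguards: the exclusion of Veterans taking thiamine supplements does not order the study draw against study-advised IV therapy. The lost-value rule does not cover a value that exists but was drawn late.

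**How much thiamine could precede the draw.** With a draw g hours after the first dose, doses given = floor(g/8) + 1, at 400 mg each. The documents do not give g.
- g under 8 h: 1 dose, 400 mg.
- g = 12 or 15 h: 2 doses, 800 mg.
- g = 16 to 21 h: 3 doses, 1,200 mg.

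The 12 to 21 h range assumes a first dose between 09:00 and 17:00 and a sample at the next morning draw. The plan does not say how far such doses raise a level. It does re-draw biomarkers at Visit 3 to look for a rise, so a rise on treatment is anticipated in direction, though not in size.

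**Effect on prevalence.** Section 15.1 divides by all enrolled, so k missed cases cost k/300. The documents do not give k; 1 to 5 is an assumed range.
- k = 1: 1/300 = 0.33 points.
- k = 3: 3/300 = 1.00 point.
- k = 5: 5/300 = 1.67 points.

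With the 255 left after the planned 15% drop-out, the same counts give 0.39, 1.18 and 1.96 points. A case is lost only if its post-dose level leaves the low-normal range, because low-normal levels also qualify.

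**Effect on the cut-points.** Section 15.2 plans on 19 responders and 38 non-responders for a symptom. At a given cut-point, one responder moved from below to above it lowers estimated sensitivity by 1/19 = 5.3 points. One non-responder moved the same way raises estimated specificity by 1/38 = 2.6 points. The distortion therefore has no fixed direction, and a few samples matter more here than for prevalence.

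**Severe patients without WE.** Footnote 1 allows repletion at Visit 1, while Table 3 marks the symptom survey and targeted exam only at Visits 2 and 3. The text of 10.1 sends these patients to Visit 2, and 10.2 describes the interview and exam first and the IV advice afterwards. The two sources disagree on when treatment starts.

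**The case against.** The strongest reply is that the plan already permits an early sample. The thiamine-specific sentence in 10.1 sets no morning requirement, and Informed Consent Process says extra blood work is matched to routine draws only where that can be done. Staff may well draw first in practice. This stands as a reason to expect few post-dose samples, but permission to draw early is not a requirement to draw before dosing.

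The affected group is also narrow: people with WE who do not drink to excess, take no thiamine and can consent. Those who temporarily lack capacity are approached only later in the stay. That stands, and it limits the size of the effect. It is also fair that the study only advises IV therapy; the primary team starts it and laboratory staff draw the blood. The study cannot guarantee the order, which is why a rule for post-dose samples is needed as well.

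Two stronger readings are tempting. A reader might infer from 10.3, which selects on low or low-normal biomarkers, that an IV-treated participant with a raised level would miss Visit 3. The documents do not support this. Section 10.2 continues oral thiamine in the IV group up to Visit 3, Data and Specimen Banking repeats the survey and exam at Visit 3 for symptomatic Veterans started on repletion, and Study Duration has those with symptoms attend.

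A reader might also infer that severe patients without WE have no exam before treatment. That follows only if footnote 1 overrides the text of 10.1 and 10.2. WE participants are examined before the advice to treat.

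**Conclusion.** The gap in the order of draw and dose is real and worth closing. As written, a post-dose level can serve as the untreated baseline in the biomarker-based outcome of 15.1 and in the cut-point analysis of 15.2. The effect on prevalence is downward and likely minor: 0.33 points per missed case on 300 enrolled, with the number affected unstated and probably small. The consequence for 15.2 could be larger per sample, though that analysis is declared exploratory.

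The effect should not be set against the plan's precision of +/- 5.4 points. That figure is stated for TDD prevalence, and the TDD definition in 15.1 needs no biomarker. Nor do the documents support assuming that a sizeable share of cases would be dosed before sampling.

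The conclusion assumes that IV thiamine can raise either biomarker within hours to a day, which the documents do not quantify. The footnote 1 discrepancy is a conflict of wording, not a demonstrated loss of baseline data.

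**What to change.** 1. Add to 10.1: *Whenever IV thiamine is advised, plasma thiamine and whole blood ThDP are drawn before the first dose; this sample need not be fasting or wait for the morning draw, and urgent treatment is not delayed if it cannot be obtained.*
2. Record the times of the first thiamine dose and of the draw. If the dose came first, treat the level as lost under the existing 10.1 rule and keep it out of the 15.2 cut-point analysis. In 15.1, report how many such participants there are, and show prevalence with them counted by symptom response and again as non-cases.
3. Align footnote 1 with the text of 10.1 and 10.2. If the investigator does intend to treat severe patients without WE at Visit 1, do the symptom survey and targeted exam before the first dose.

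The cost is a few sentences, one footnote edit, two time fields and an occasional extra needle stick. Some of these baseline samples will not be fasting. Treatment and the number of visits do not change.
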